### **PARTICIPANT ADVERSE EVENT REPORTING PROCEDURES.**

CONFIDENTIAL

This material is the property of the University of Pennsylvania. Do not disclose or use except as authorized in writing by the study sponsor

For any reported adverse event: While with the participant, study personnel will listen, identify, and document the adverse event, which may not be related to medication and may not be a Serious Adverse Event. The protocol for recording adverse events and reporting the event is listed below:

- The symptom **MUST** be coded by its severity and responded to according to the following protocol (please see tables below for symptom coding).
- **Severity Definitions:** None = no concerns, Mild = Adverse event does not interfere with usual daily activities; Moderate = Adverse event interferes with some activities; Severe = No normal activities are possible.

	Code 1 Response	Code 2 Response	Code 3 Response	Code 4 Response
Adverse Event Checklist: If adverse event severity is not listed, no report is required unless the participant requests that the study physician be consulted.				
1. Irritability		Moderate	Severe	
2. Irregular heartbeat		Mild Moderate	Severe	
3. Depressed mood	Mild	Moderate	Severe	
4. Increased heart rate or palpitations		Mild Moderate	Severe	
5. Suicidal thoughts, ideation			Any Reporting	
5b. Suicide Attempt				Any Reporting
6. Nausea (without vomiting)		Moderate	Severe	
7. Sleep problems		Moderate	Severe	
8. Constipation		Moderate	Severe	
9. Vomiting		Mild Moderate Severe		
10. Dry Mouth		Moderate	Severe	
11. Gas		Moderate	Severe	
12. Anxiety		Moderate	Severe	
13. Skin swelling or rash		Moderate	Severe	
14. Indigestion		Moderate	Severe	
15. Agitation		Mild	Moderate Severe	
16. Insomnia		Moderate	Severe	
17. Headache		Moderate	Severe	
18. Abnormal dreams		Moderate	Severe	
19. Disturbance in Attention		Moderate	Severe	
20. Diarrhea		Severe		
21. Abdominal Pain	Mild	Moderate	Severe	
22. Flatulence		Moderate	Severe	
23. Dizziness		Moderate	Severe	
24. Fatigue		Moderate	Severe	
25. Feeling of Weakness		Moderate	Severe	
26. Skin Redness		Moderate	Severe	
27. Hostility		Mild	Moderate Severe	
28. Chest pain		Mild Moderate	Severe	

CONFIDENTIAL

This material is the property of the University of Pennsylvania. Do not disclose or use except as authorized in writing by the study sponsor

29. Weakness of one or both sides of the body		Mild Moderate	Severe	
30. Blurred vision		Mild Moderate	Severe	
31. Sweating			Severe	
32. Strange taste			Severe	
33. Ringing in ears		Mild Moderate	Severe	
34. Tremors		Mild Moderate	Severe	
35. Seizure				Any Reporting
36. Fainting (loss of consciousness)			Any Reporting	
37. Confusion		Moderate	Severe	
38. Muscle aches		Moderate	Severe	
39. Shortness of Breath		Mild	Moderate Severe	
Open-ended Responses (this is not an exhaustive list)				
1. Allergic reaction	Mild	Moderate	Severe	
2. Appetite loss	Moderate	Severe		
3. Asthma		Moderate	Severe	
4. Blood pressure increase		Moderate	Severe	
5. Cancer				Any Reporting
6. Change in taste perception		Moderate	Severe	
7. Chest pain		Mild	Moderate Severe	
8. Trouble concentrating		Moderate	Severe	
9. Death				Any Reporting
10. Emergency Room Visit				Any Reporting
11. Heart Attack/MI				Any Reporting
12. Heartburn		Moderate	Severe	
13. Hospitalization				Any Reporting
14. Itching		Moderate	Severe	
15. Lightheadedness	Mild	Moderate Severe		
16. Nose Bleed		Moderate Severe		
17. Neurological event Stroke/TIA, etc				Any Reporting
18. Psychiatric event (not related to suicide)		Mild	Moderate Severe	
19. Racing thoughts		Moderate	Severe	
20. Runny nose		Moderate	Severe	
21. Sore throat		Moderate	Severe	

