## **PARTICIPANT SAFETY MONITORING PROTOCOL**

**Monitoring Participant Safety.** For this trial, we will use a method to track, manage, and report adverse events that was used in completed studies (14, 43, 52) and is being used in an ongoing (U01 DA020830) pharmacotherapy trial. First, in terms of personnel, each clinical site will include a study physician, a study psychologist, and a research nurse/qualified medical staff person to handle comprehensive eligibility screening, monitoring of participant reactions and adverse events, and the management of any adverse events. The initial eligibility screening procedures will involve careful assessment of participants' medical history to ensure that individuals with pre-existing conditions that can increase adverse event risk are excluded. Second, we will use a two-tiered system to assess potential adverse events. Site staff will complete a baseline adverse event checklist (week 0). At weeks 1, 3, 5, 7, and 10, staff members will conduct an open-ended evaluation of any potential adverse event and complete the established checklist of adverse events. Lastly, as done in our previous clinical trials, participants will be provided with contact information (a wallet-size card) so that, if a serious adverse event occurs, they have methods to contact study staff at their respective clinical site 24 hours a day. Because participants may try to communicate regarding adverse events through the daily text messaging service, which will not be monitored for this purpose, we will provide contact information via an auto-message informing the participant of how to reach study staff in an emergency.

For all adverse events, the site nurse practitioner, in consultation with the site PI and the obstetrician at each site (as needed), will determine a course of action (i.e., continuation and monitoring, dose reduction, participant withdrawal). All adverse events that are considered Serious Adverse Events (see below) will be reported to site PIs and IRBs at all clinical sites, as well as to the FDA and NIH (see below for protocol for adverse event reporting). Site PIs and study physicians will determine whether a serious adverse event requires additional care. Such events may be referred to the outpatient department at the clinical site or to the emergency department of the clinical site (all sites have access to 24-hour emergency services, including extensive inpatient and outpatient services for psychiatric conditions).

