### **Code 2 Events**

- Documented either on Adverse Event Checklist or on Open-Ended SE Form
- If reported at a scheduled visit, email sent to Site PI, Site Study Physician, and Site Coordinator for review within **24 hours** (obstetrician to be consulted, as needed).

Email should be based on the following template:

*Today, an adverse events assessment with participant XXXXXXXX was completed. This session was conducted at week X, X weeks after study medication was initiated. During the assessment the participant reported [mild/moderate/severe] \_\_\_\_\_ (Code X).*

*This adverse event was (or was not) reported at a previous assessment.*

*The participant is currently/not currently smoking and is/is not on protocol with taking study medication. Please let me know whether - after your review - the SEC codes should be modified &/or if further action should be taken.*

- Internally reviewed by the site PI and/or Study Physician.
  - Response printed out and filed in the participant's research chart.
  - Participant may continue medication unless she thinks that the medication is making her symptoms worse or wants to stop (or the Study Physician tells her to stop).
  - Dose adjustments can also be considered.
  - The Study Physician will follow-up with the participant as deemed appropriate.
- The study physician/PI can evaluate the information presented in the email along with any further information received from contact with the participant and, based on clinical

CONFIDENTIAL

judgment, change the code that the event received (either increasing in severity or decreasing in severity). The SEC data may be changed accordingly.

If reported to site staff **between scheduled sessions**, email sent to PI, Study Physician, and Study Coordinator for review within 24 hours as above

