### **Code 3 Events**

- Regardless of when Code 3 events are reported, they will be considered urgent and follow-up will be immediate.
- Staff can advise participants to contact their physician immediately or call 911.
- If the participant is currently taking study medication, she will be instructed to discontinue the medication pending additional consultation with her doctor or a Study Physician.
- ***If reported during a visit, the site physician and/or PI will be notified immediately by phone or in-person to address the report immediately (see template below for call).*** The physician may be contacted via pager so that the situation can be resolved quickly. The study doctor will evaluate the problem and, if needed, contact the maternal-fetal medicine attending (during regular hours) or the maternal-fetal medicine fellow on-call (during off hours).
- An email is also sent for documentation as follows to the study physician, PI and coordinator.

Email (or conversation) should be based on the following template:

*Today, an adverse events assessment with participant XXXXXXXX was completed. This session was conducted at week X, X weeks after study medication was initiated. During the assessment the participant reported [mild/moderate/severe] \_\_\_\_\_ (Code X).*

*This adverse event was (or was not) reported at a previous assessment.*

*The participant is currently/not currently smoking and is/is not on protocol with taking study medication. Please let me know if - after your review - the SEC codes should be modified &/or if further action should be taken.*

- Study Physician will oversee recommendations and follow-up with the participant until the event is resolved or the participant is stable.
- Study Physician will report to the PI.
- Response printed out (or conversation documented) and filed in the participant's research chart.
- The physician can evaluate the information presented in the email/telephone call or in-person assessment along with any further information received from contact with the participant and, based on clinical judgment, change the code that the event received (either increasing in severity or decreasing in severity). The SEC data may be changed accordingly.
- These events may be considered Serious Adverse Events, requiring additional reporting

CONFIDENTIAL

(see below).

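### Moderate chest pain is Code 2 on the adverse-event checklist but Code 3 on the open-ended list, with no stated rule for which code governs

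*Combined protocol and SAP*

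**What the plan says.** Section 10.1, under Participant Adverse Event Reporting Procedures, gives a table that assigns each symptom and severity to a response code from 1 to 4. The text above the table requires each symptom to "be coded by its severity and responded to according to the following protocol". One set of definitions for mild, moderate and severe applies to both parts of the table.

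Chest pain appears in both parts:

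- Adverse Event Checklist: "28. Chest pain Mild Moderate Severe". Mild and moderate share the Code 2 column, and severe is in the Code 3 column.
- Open-ended Responses: "7. Chest pain Mild Moderate Severe". Mild is in the Code 2 column, and moderate and severe share the Code 3 column.

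The words in the two rows are the same. They differ in the column that holds moderate.

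The Participant Safety Monitoring Protocol uses both instruments at weeks 1, 3, 5, 7 and 10, when "staff members will conduct an open-ended evaluation of any potential adverse event and complete the established checklist of adverse events".

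The codes lead to different responses. Under Code 2 Events, an email goes out for review within 24 hours and the woman may stay on study drug "unless she thinks that the medication is making her symptoms worse or wants to stop (or the Study Physician tells her to stop"). Under Code 3 Events, "they will be considered urgent and follow-up will be immediate", the physician or principal investigator is notified at once, and if she is taking study drug "she will be instructed to discontinue the medication pending additional consultation with her doctor or a Study Physician".

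Clinicians keep control after that. For every adverse event the site nurse practitioner, consulting the site principal investigator and obstetrician as needed, "will determine a course of action (i.e., continuation and monitoring, dose reduction, participant withdrawal"). The physician may also raise or lower the code.

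**The concern.** A response table works only if one event leads to one response. Here the same complaint at the same severity leads to two, and they differ in the two things the code controls: how soon a physician is told, and what the woman is told to do with her tablets meanwhile.

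Sections 6.4, 6.6 and 6.12 allow a coordinator, under nurse or physician supervision, to record adverse events, so the person applying the table may not be a clinician. Table 2 schedules the week 3 and week 7 assessments by telephone, where the written code carries more weight because nobody can examine her. Chest pain may be cardiac, and the participants are pregnant. Section 1.5 lists hypertension among the frequent reactions to bupropion, and tachycardia and stroke among the infrequent ones.

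What is at stake is consistent participant protection in the interval before a clinician decides. Trial validity is not at stake.

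**Working it through.** The plan gives no figure to reproduce on this point. The check sets the two rows and the two response rules side by side, looks for a rule that settles the conflict, and then sizes it.

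**1. The two rows, read by column**

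| Severity | Checklist item 28 | Open-ended item 7 | Agree? |
|---|---|---|---|
| Mild | Code 2 | Code 2 | yes |
| Moderate | Code 2 | Code 3 | no |
| Severe | Code 3 | Code 3 | yes |

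The difference does not look like a fault in reading the table. Item 28 has the same column pattern as irregular heartbeat and palpitations. Item 7 has the same pattern as agitation, hostility and shortness of breath.

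**2. What each code triggers**

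| | Code 2 | Code 3 |
|---|---|---|
| Review | email, within 24 hours | immediate, by phone or in person |
| Study drug meanwhile | may continue, with the exceptions quoted above | told to stop pending consultation |
| Advice to contact own physician or call 911 | not mentioned | staff can give it |
| Possible serious adverse event flagged | not mentioned | yes |

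**3. Is there a tie-break?**

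- Measures for Participant Safety says the open-ended questions add to the standard measures so that unexpected events are caught. That is a purpose, not an order of precedence, and the open-ended list itself names chest pain.
- Code 2 Events allows documentation on either form.
- The steps under Diagram of Protocol name only the checklist, as the tool for identifying and grading an event. They do not say whose code applies.
- Neighbouring checklist rows point both ways: moderate irregular heartbeat and moderate palpitations are Code 2, while moderate shortness of breath is Code 3.
- Physician recoding acts after the starting code has already set the speed of notification and the interim drug instruction.

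**4. Size**

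- Table rows: checklist items 1 to 39 plus 5b = 40, and open-ended items = 21. Total 40 + 21 = 61.
- Symptoms named identically in both lists: 1 (chest pain). Severity grades in conflict: 1 of 3.
- Further dosing under Code 2 before review, at 150 mg twice daily (Study Summary) and assuming review is complete within 24 hours: at most 2 × 150 mg = 300 mg. It is zero if review is prompt.
- Scheduled assessments affected: review speed at all 5. Drug action at 4 (weeks 1, 3, 5 and 7), since Table 1 shows no medication from week 10.
- The documents give no rate of moderate chest pain, so the number of women affected cannot be estimated.

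**The case against.** The best reply is that the checklist is implicitly primary. The reporting steps name only the checklist, the open-ended questions are described as a supplement, and a symptom already on the checklist is not unexpected. This is a reasonable guess at intent, but it is not stated, and it does not explain why chest pain has its own open-ended row with a different code.

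Second, both instruments are completed for every woman at each scheduled assessment, so women are not divided between forms and staff may see both codes. That stands: divergent handling is possible, not automatic. But staff who see both rows then hold two conflicting mandatory instructions.

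Third, clinicians set the course of action for every event, a study physician is available at all times (Section 8.6), weeks 3 and 7 may be done in person (Sections 6.5 and 6.7), and 24 hours is a ceiling. All of this is correct and limits the effect to the period before clinical review. It does not remove the conflict within that period.

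Fourth, the choice of Code 3 is clinical, and the plan does place other moderate cardiac-type symptoms at Code 2. That stands, so the code should be confirmed by the study clinicians.

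Finally, the reporting diagram and some pages of the safety section were not available for this check. The claim is therefore that no precedence rule appears in the text that could be read.

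**Conclusion.** The contradiction is real and should be fixed. For moderate chest pain the table as written cannot give a single response. One row means review within 24 hours with study drug continuing by default, and the other means immediate contact with study drug stopped.

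The effect is narrow: one symptom, one severity grade, and only the interval before a clinician decides, with at most two further doses if review is complete within 24 hours. H2 is unaffected because its outcome depends on severity, and moderate is moderate on either row. The definition of a serious adverse event does not depend on which row is used. An emergency room visit, hospitalization or heart attack is Code 4 in any case.

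The conclusion rests on the column positions in the table and on there being no precedence rule in the parts of the safety section that could not be read.

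**What to change.** Give moderate chest pain the same code in both lists. Code 3 is the more cautious choice, and the study physician and study obstetrician should confirm it. Add one sentence to Section 10.1: when an event fits both lists, the higher code governs until physician review.

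The near-synonym rows (dizziness and lightheadedness, strange taste and change in taste perception) can be checked in the same edit. Their names differ, so they are not strict contradictions.

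The cost is a wording amendment to one table row, one added sentence and a corrected code sheet for the sites, with no new procedures, staff or participants. If Code 3 is chosen, each moderate chest-pain report now coded from the checklist will need an immediate physician call, and a woman still on study drug will be told to stop pending that consultation.

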### **Code 1 Events**

- Documented either on Adverse Event Checklist or on Open-Ended AE Form
- If reported at a scheduled visit, email sent to Site PI, Site Study Physician, and Site Coordinator for review within **72 hours**

Email should be based on the following template:

CONFIDENTIAL

This material is the property of the University of Pennsylvania. Do not disclose or use except as authorized in writing by the study sponsor

*Today, an adverse event assessment with participant XXXXXXXX was completed. This session was conducted at week X, X weeks after study medication was initiated. During the assessment the participant reported [mild/moderate/severe] \_\_\_\_\_ (Code X).*

*This adverse event was (or was not) reported at a previous assessment.*

*The participant is currently/not currently smoking and is/is not on protocol with taking study medication.*

- Internally reviewed by the PI and/or Study Physician.
  - Response printed out and filed in the participant chart.
  - The participant will continue in the trial unless they decline to do so. Medication can be continued.
- The physician can evaluate the information presented in the email along with any further information received from contact with the participant and, based on clinical judgment, change the code that the event received (either increasing in severity or decreasing in severity).
  - If reported to site staff **between scheduled sessions**, email sent to PI, Study Physician, and Study Coordinator for review within 48 hours as above.

### **Code 2 Events**

- Documented either on Adverse Event Checklist or on Open-Ended SE Form
- If reported at a scheduled visit, email sent to Site PI, Site Study Physician, and Site Coordinator for review within **24 hours** (obstetrician to be consulted, as needed).

Email should be based on the following template:

*Today, an adverse events assessment with participant XXXXXXXX was completed. This session was conducted at week X, X weeks after study medication was initiated. During the assessment the participant reported [mild/moderate/severe] \_\_\_\_\_ (Code X).*

*This adverse event was (or was not) reported at a previous assessment.*

*The participant is currently/not currently smoking and is/is not on protocol with taking study medication. Please let me know whether - after your review - the SEC codes should be modified &/or if further action should be taken.*

- Internally reviewed by the site PI and/or Study Physician.
  - Response printed out and filed in the participant's research chart.
  - Participant may continue medication unless she thinks that the medication is making her symptoms worse or wants to stop (or the Study Physician tells her to stop).
  - Dose adjustments can also be considered.
  - The Study Physician will follow-up with the participant as deemed appropriate.
- The study physician/PI can evaluate the information presented in the email along with any further information received from contact with the participant and, based on clinical

CONFIDENTIAL

judgment, change the code that the event received (either increasing in severity or decreasing in severity). The SEC data may be changed accordingly.

If reported to site staff **between scheduled sessions**, email sent to PI, Study Physician, and Study Coordinator for review within 24 hours as above

### **Code 3 Events**

- Regardless of when Code 3 events are reported, they will be considered urgent and follow-up will be immediate.
- Staff can advise participants to contact their physician immediately or call 911.
- If the participant is currently taking study medication, she will be instructed to discontinue the medication pending additional consultation with her doctor or a Study Physician.
- ***If reported during a visit, the site physician and/or PI will be notified immediately by phone or in-person to address the report immediately (see template below for call).*** The physician may be contacted via pager so that the situation can be resolved quickly. The study doctor will evaluate the problem and, if needed, contact the maternal-fetal medicine attending (during regular hours) or the maternal-fetal medicine fellow on-call (during off hours).
- An email is also sent for documentation as follows to the study physician, PI and coordinator.

Email (or conversation) should be based on the following template:

*Today, an adverse events assessment with participant XXXXXXXX was completed. This session was conducted at week X, X weeks after study medication was initiated. During the assessment the participant reported [mild/moderate/severe] \_\_\_\_\_ (Code X).*

*This adverse event was (or was not) reported at a previous assessment.*

*The participant is currently/not currently smoking and is/is not on protocol with taking study medication. Please let me know if - after your review - the SEC codes should be modified &/or if further action should be taken.*

- Study Physician will oversee recommendations and follow-up with the participant until the event is resolved or the participant is stable.
- Study Physician will report to the PI.
- Response printed out (or conversation documented) and filed in the participant's research chart.
- The physician can evaluate the information presented in the email/telephone call or in-person assessment along with any further information received from contact with the participant and, based on clinical judgment, change the code that the event received (either increasing in severity or decreasing in severity). The SEC data may be changed accordingly.
- These events may be considered Serious Adverse Events, requiring additional reporting

CONFIDENTIAL

(see below).

- If reported to site staff **between scheduled sessions**, email or phone call to PI, Study Physician, and Study Coordinator for review immediately, following the procedures above.

